4. ANALYSIS POPULATIONS

4.1 Analysis Populations

Safety Population: All subjects who received at least one dose of the study drug will be included in the safety evaluations.

PK Population: All subjects who comply sufficiently with the protocol and display an evaluable PK profile (e.g., exposure to treatment, availability of measurements and absence of major protocol violations) will be included in the statistical analyses.

Pharmacodynamic/Target Engagement: All subjects who complete the study will be included in the pharmacodynamics/target engagement analysis.

Muscle/Motor Function (Grade Functional Tests and MFM32): All subjects who complete the study will be included in the muscle/motor function assessments.

Quality of Life: All subjects who complete the study will be included in the quality of life assessments.

4.2 Preliminary Data and Interim Analysis

Interim PK analysis will be conducted by Nuvisan (contract vendor) as follows:

First dose group (120 mg/day): Full PK analysis (see Table 6:1 for PK parameters) once the first three participants have completed dosing for 28 days. This will allow verification that the observed PK results from these RYR1-RM affected individuals agree with PK results from previous studies in healthy volunteers and that the Cmax limit [REDACTED] was not exceeded. At this stage of drug development, a PK value that would not require a dose adjustment would be considered as similar. This would mean 50% lower or 200% higher than that of healthy volunteers. Based on PK results and safety data from the first dose group, the dose to be administered in subsequent

participants may be increased to \leq 200 mg/day. This will be based on DSMB recommendations and investigator and sponsor's joint decision.

Second dose group (\leq 200 mg/day): PK analysis for Cmax once the first three participants have completed dosing for 28 days. This will allow verification that the Cmax limit [REDACTED] was not exceeded. If this is the case, then all remaining samples will be shipped to the contract laboratory for analysis at the end of the study, when full PK analysis beyond the Cmax measurement will occur for all of the samples obtained from this group.

5. TREATMENT DESCRIPTIONS

S 48168 (ARM210) requires an IND, and the FDA approved IND number is: [REDACTED]. The company manufacturing S 48168 (ARM210) is Laboratoires Servier. Study drug will be shipped by Laboratoires Servier directly to the NIH Pharmacy as therapeutic units. The study sponsor is ARMGO Pharma Inc.

S 48168 (ARM210) will be supplied as 20 mg gastro-resistant tablets ([REDACTED]).

Table 5.1 Description of Treatments

Treatment	Short Description (text, tables, figures, listings, SAS output)	Abbreviated Description (footnotes)
Sponsor Protocol: [REDACTED]		
A	Single oral 120 mg S 48168 (ARM210) QD for 28 days (patients)	Single oral 120 mg S 48168 (ARM210) (6 x 20 mg tablets) daily for 28 days (patients)
B	Single oral 200 mg S 48168 (ARM210) QD for 28 days (patients)	Single oral 200 mg S 48168 (ARM210) (10 x 20 mg tablets) daily for 28 days (patients)
Sponsor Protocol: [REDACTED]		
C	Single oral 120 mg S 48168 (ARM210) QD for 14 days (healthy subjects)	Single oral 120 mg S 48168 (ARM210) (3 x 40 mg tablets) daily for 14 days (healthy subjects)
D	Single oral 240 mg S 48168 (ARM210) QD for 14 days (healthy subjects)	Single oral 240 mg S 48168 (ARM210) (1 x 200 mg and 1 x 40 mg tablets) daily for 14 days (healthy subjects)

6. SAFETY

All case report form (CRF) data will be listed by subject and chronologically by assessment time points. This will include rechecks, unscheduled assessments, and early termination.

Applicable continuous variables will be summarized using n, arithmetic mean, SD, minimum, median, and maximum. Frequencies and percentages will be used to summarize categorical variables.

The level of precision will be presented as follows: minimum/maximum in the same precision as in the database, mean/median in one more precision level than minimum/maximum, SD in one more precision level than mean/median, and n will be presented as an integer.

Where individual data points are missing because of dropouts or other reasons, the data will be summarized based on reduced denominators.

6.1 Subject Discontinuation

Subjects will be summarized by number of subjects enrolled, completed, and discontinued the study with discontinuation reasons by treatment and study overall.

6.2 Demographics

Descriptive statistics will be calculated for continuous variables (age, weight, height, and body mass index) by treatment and study overall.

Frequency counts will be provided for categorical variables (race, ethnicity, and sex) for each treatment and study overall.

6.3 Adverse Events

All adverse events (AEs) reported during this clinical trial will be coded using the Medical Dictionary for Regulatory Activities (MedDRA[®]), Version 21.0.

All adverse events will be reviewed by the Medical Monitor and graded in accordance with CTCAE version 5

(https://ctep.cancer.gov/protocoldevelopment/electronic_applications/ctc.htm)

All AEs captured in the database will be listed in by-subject data listings including verbatim term, coded term, treatment, severity, relationship to study medication, and action; however, only treatment-emergent AEs (TEAEs) will be summarized.

A TEAE is defined as an AE that is starting or worsening at the time of or after study drug administration. Each TEAE will be attributed to a treatment based on the onset date and time of the AE.

An AE will also be considered treatment emergent if: onset date of an AE is missing; if onset time of an AE is missing and the onset date is the same as the treatment dosing date; and if both AE onset date and time are missing.

TEAEs will be tabulated by System Organ Class (SOC) and Preferred Term (PT). Summary tables will include number of subjects reporting the AE and as percent of number of subjects dosed by treatment and study overall. The number of AEs will be tabulated in a similar manner. Tables which tabulate the number of TEAEs by severity and relationship to study treatment will also be included.

Serious adverse events (SAEs), if present, will also be listed. Applicable narratives will be included in the CSR.

Frequencies of TEAEs \geq grade 2 in severity (CTCAE version 5), all SAEs, and all AE of Special Interest (AESI) will be tabulated by SOC/TE.

The frequency and severity of clinically significant AEs will be compared descriptively between treatment and historical controls including a previously conducted natural history study at the NIH.

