71	
Subject information and consent: The first paragraph has been revised to clarify that blood obtained under the telephone consent will be used to test for CYP2C8 and serology.

72-73	
Management of data and samples: NINR Tissue Injury Branch has been added as a location for sample storage.
 
The following language has been removed:
 
(1): “De-identified, unlinked skeletal muscle tissue samples will be collected and transported to the NINDS Neurogenetics Branch (building 35) for storage, ahead of analyses described in the biopsy manual”
 
(2): “after the completion of the first 5 patients and after the completion of the 5 last patients”.
 
(3): “and/or submitted to NIH designated repositories and databases”
 
(4): “repositories receiving data and/or samples from this protocol may be open-access or restricted access”
 
(5): “Submissions to NIH-sponsored or supported databases and repositories will be reported at the time of Continuing Review. Submission to non-NIH sponsored or supported databases and repositories will be submitted for prospective IRB approval.”

Amendment 3 (expedited)	
4, 12-16, 21, 30-31, 35, 37, 48- 49, 55-57, 64, 67, 69	Dosing period was changed from “28 days” to “28 not to exceed 30 days” throughout the protocol
Amendment 4	
12, 16, 41- 43, 51, 66	Muscle biopsy RyR1-calstabin1 assay (inclusion criterion) was deleted and reference to this removed throughout the protocol
Amendment 5	
17, 41, 43- 44, 51, 56	Removal of skeletal muscle needle biopsy procedure for subject 0007 and subsequent participants, including all reference to this
47	Muscle biopsy-specific inclusion/exclusion criteria removed

15, 18, 40, 41, 65	Removal of 24hour PK study for subjects who have been previously dosed and are therefore not drug naïve
15, 17, 23, 39-41	Switch in-person study visit on Day 14 to remote assessments and labs
19, 33	Removal of Day 14 EKG
67	Anticipated blood draw volumes added for re-enrolled subjects
17, 21, 22, 39 41	Switch Day 42 remote follow-up to an in-person study visit with efficacy assessments. Schedule of activities was updated accordingly
15, 20, 22, 37, 43	Addition of quantitative muscle assessment (QMA) to the battery of physical therapy tests
54, 55	Updated description of consent process for re-enrolled subjects
17, 39	Updated Figure 1 to reflect Amendment 5 changes
30, 31, 59	Updated reference to the IB to 2020 version

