A new class of Ca^{2+} channel stabilizers, Rycals®, were developed by [name] at Columbia University. Under normal physiological conditions, Calstabin1 binds and stabilizes the RyR1 closed state. Rycals function as Ca^{2+} channel stabilizers by restoring RyR1-Calstabin1 binding when it is deficient, thereby stabilizing the RyR1 closed state. To date, [name] laboratory has tested Rycals pre-clinically in at least 20 *RYR1*-RM patient muscle biopsies *in vitro*, including ten obtained during a previous clinical trial (NCT02362425). All untreated samples initially showed decreased RyR1-Calstabin1 binding (<10- 40% of healthy control muscle), which improved to 70-90% of control levels upon treatment with Rycals *ex vivo*. This work has demonstrated that Rycal treatment can restore RyR1-Calstabin1 binding and rescue leaky RyR1 channels in human biopsies *ex vivo*. In addition, a few muscle disease mouse models demonstrated that Rycal treatment improved muscle strength and muscle cell survival and may therefore offer a promising treatment for *RYR1*-RM (Andersson and Marks, 2010; Capogrosso et al. 2018; Wanig et al. 2015). S 48168 may also have benefit for malignant hyperthermia susceptibility, a condition allelic to *RYR1*-RM, by restoring the conformational integrity of mutant RyR1 channels. The lead Rycal, S 48168 (ARM210), has completed Phase I clinical studies in healthy volunteers. In those studies, S 48168 (ARM210) was safe and well tolerated in single and multiple dose studies and has now been tested in six (6) patients with *RYR1*-RM. This study continues to test S 48168 (ARM210) in a Phase I trial in *RYR1*-RM patients.

The objectives of this study are to explore the safety and tolerability, pharmacokinetics (PK), pharmacodynamics (PD)/target engagement (TE) of S 48168 (ARM210), as well as effects on muscle/motor function, and fatigue in adult *RYR1*-RM patients. The open-label study design consists of approximately 8-20 participants and two dose groups. The first three participants received 120 mg S 48168 (ARM210) daily for approximately 28 (not to exceed 30) days. Three participants have been enrolled in the second group and received 200 mg S 48168 (ARM210) daily for approximately 28 (not to exceed 30) days. The decision to escalate to a top dose of 200 mg daily was made by an independent Data and Safety Monitoring Board (DSMB) after

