	
Hypothesis: There will be no clinically meaningful difference in S 48168 (ARM210) exposure at steady state in RYR1-RM affected individuals when compared to existing data established in healthy volunteers.
 
Endpoints:
 
S 48168 (ARM210) pharmacokinetics
 
Day 1 composite PK profile (drug naïve individuals only)
 
(Comprised of the following: AUC0-t, AUC0-inf, Cmax, Tmax, and t_{1/2}).
 
Day 28 (not to exceed Day 30) composite PK profile
 
(Comprised of the following: AU_{tau}, Cmax, Tmax, Cmin, RAAUC, and RACmax).
 
Methods: For participants who have not been dosed previously (i.e., drug naïve individuals), bloods for PK assessments will be drawn at study visit one (Day 0, 24h PK), study visit two (Day 28; not to exceed Day 30, 24h PK). For individuals who have been dosed previously, a 24hr PK assessment at Day 0 will not be required. Whole blood will be processed, and the plasma fraction stored for PK analyses.
 
2. To explore if S 48168 (ARM210) treatment increases RyR1-calstabin1 binding in skeletal muscle of RYR1-RM affected individuals.
 
Hypothesis: S 48168 (ARM210) treatment will increase RyR1-calstabin1 binding, compared to baseline, as determined by co-immunoprecipitation of RyR1 and calstabin1 and decrease relative Fluo-4 signal compared to baseline.
 
Endpoints: Change from baseline in relative RyR1-calstabin1 binding (AU) and (pending sufficient tissue yield) change from baseline in relative Fluo-4 signal (AU).
 
Methods: Skeletal muscle tissue was obtained from the first six participants by needle biopsy. This tissue has been assessed for RyR1-calstabin1 binding by co-immunoprecipitation followed by protein detection. Additional biopsies are not needed.
 
3. To explore if S 48168 (ARM210) treatment improves muscle function, motor activity, and fatigue in RYR1-RM affected individuals.
 
Hypothesis: Treatment with S 48168 (ARM210) will increase grip and pinch strength, increase strength as determined by quantitative muscle assessment, decrease the time it takes to complete graded functional tests, increase the total MFM-32 % maximum score, and decrease the PROMIS-fatigue subscale score, when compared to baseline.
 
Endpoints: Grip strength (kg), pinch strength (kg), quantitative muscle strength assessment (kg), time taken to complete each of the following (seconds): walk 10-meters, supine to stand, ascend 4 stairs, and descend 4 stairs, MFM-32 score for domains 1, 2, 3, and total (% of maximum score), PROMIS-fatigue subscale score (t-score).
 
Methods:

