9.5 Dose Justification

The initial proposed dose for this study was 120 mg S 48168 (ARM210) daily for approximately 28 days (not to exceed 30 days) for the first three participants (6 x 20 mg tablets) (see details outlining dose modification in Section 9.6). An additional three participants were dosed with 200 mg S 48168 (ARM210) (10 x 20 mg tablets) daily for approximately 28 days (not to exceed 30 days) after DSMB evaluation of the interim safety and PK data. The remainder of participants will be dosed at the same high dose \leq 200 mg S 48168 (ARM210) (10 x 20 mg tablets) daily for approximately 28 days. The projected exposure at 200 mg/day dose remains below preclinical safety margins ($C_{max} < 35$ ug/ml), as well as below the highest dose tested in healthy volunteers (240 mg/day for 14 days). Preclinically, the one finding that is not monitorable in humans is the proconvulsant risk, with convulsions rarely observed at highest dose level in dogs in the 39-week study. The convulsions occurred at the high dose of 250 mg/kg/day in the 39-week GLP chronic study. The C_{max} of that dose for both genders is 374 ug/ml. This concentration range is associated with an *in vivo* unbound fraction of 3.5%, which is greater than 20-fold higher than the *in vivo* fraction unbound (0.16%) in the human at 240 mg. It is likely that this high unbound fraction, which is able to penetrate tissues, including the brain, was responsible for the rare convulsions seen in 1 of 20 dogs (i.e. 1/12 dogs from the 39-week study and 0/8 dogs from the 13-week study, both studies at 250 mg/kg/day). The FDA has determined that the high dose (250 mg/kg/day from 13-week dog study) sets the NOEL for convulsions for this trial. The C_{max} at the NOEL (from the 250 mg/kg high dose) from the 13-week dog study is a mean of 320 ug/ml for both sexes. In consultation with the FDA, the current dose cap is at 35 ug/ml for C_{max} to provide a significant margin to the NOEL C_{max} from the dog.

In the first in man study [REDACTED] 40 male healthy volunteers (5 groups, approximately 8 participants per group) : placebo) completed the study part I (single escalating dose). Five dose levels were tested successively: 20 mg, 60 mg, 120 mg, 240 mg and 400 mg. In part II, four dose levels were studied with daily doses for 14 days (20 mg/day, 60 mg/day, 120 mg/day and 240 mg/day) all of which were well tolerated.

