11 INVESTIGATIONAL PLAN

11.1 Overall Study Design and Plan

This is a Phase 1, single-site, open label, safety and tolerability, PK, and PD trial of S 48168 (ARM210) with approximately 8-20 individuals with *RYR1*-RM completing the study. Participants will be dosed for approximately 28 days (not to exceed 30 days) at 120 mg or 200 mg daily of S 48168 (ARM210). To date, three participants have been dose at 120 mg and three have been dosed at 200 mg. This study is being conducted in the US at the National Institutes of Health (NIH) in the Neurogenetics Branch of NINDS in collaboration with ARMGO Pharma Inc (the Sponsor), and Les Laboratoires Servier.

The overall design of the study is shown below (Figure1)

[figure not shown]

Figure 1: Study Design

For each participant, the study duration will be approximately 2 months from enrollment to completion. Overall there will be three visits at the NIH CC, Bethesda, MD; one prior to the first dose, one at the end of the dosing period, and one approximately 2 weeks after cessation of S 48168 (ARM210). The last visit will include a blood draw for safety labs, and the full battery of exploratory efficacy assessments. Study participants are contacted by telephone/secured email approximately weekly for a follow-up regarding AEs and can also describe daily any symptoms in a subject diary. Follow-ups will serve to encourage study compliance. The dosing interval for S 48168 (ARM210) will be approximately 28 days (not to exceed 30 days). A study investigator will contact participants by telephone to remind them of upcoming, scheduled local phlebotomy appointments if relevant.

Safety will be monitored throughout the study by repeated clinical and laboratory evaluations.

Discontinued subjects may be replaced at the discretion of the Sponsor in consultation with the PI and DSMB. The pre-screening accrual ceiling will be up to 50 subjects with a target number of approximately 8-20 completers.

Overview of study visits:

Pre-screening of individuals will be conducted by the study coordinator who will use prior medical records and biospecimen data and/or an IRB-approved script (Appendix # 2). During pre-screening, interested individuals may be asked pre-specified questions pertaining to the inclusion and exclusion criteria if needed.

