8. PHARMACODYNAMICS/TARGET ENGAGEMENT AND MOTOR FUNCTIONS

8.1 Pharmacodynamic/Target Engagement (Exploratory):

All participants will undergo two needle muscle biopsies during the study in order to determine S 48168 (ARM210) PD in the RYR1-RM population. Biopsy 1 will take place pre-dose during study visit 1 (Day -1/Day 1, pre-treatment). Biopsy 2 will take place during study visit 3 (Day 27/28, post-treatment). Baseline (pre-treatment) and

post-treatment biopsies will be assayed for RyR1-Calstabin1 interaction as % RyR1-Calstabin1 binding of normal control muscle. % RyR1-Calstabin1 binding will be listed by subject with summary statistics calculated to compare between pre- and post-treatment biopsy results.

If there is sufficient remaining tissue, % Ca^{2+} leak from RyR1 will be determined and listed by subject and compared between pre- and post-treatment biopsies.

8.2 Motor Functions and Quality of Life (Exploratory):

Timed Functional Tests: Timed functional tests will be performed on Day -1 (pre-treatment) and Day 27 (post-treatment) and include 10-meter walk test, supine to stand, ascend 4 stairs, and descend 4 stairs. The recorded time will be listed by subject and summarized descriptively for each test to compare between pre- and post-treatment biopsy results.

Grip/Pinch Strength: Day -1 versus Day 27 hand grip and pinch strength will be documented quantitatively using dynamometry. This will also be assessed at trial mid-point (Day 14). The results will be listed by subject and summarized descriptively to compare hand grip and pinch strength (kg) between pre- and post-treatment.

Motor Function Measure 32:

Day -1 versus Day 27 motor function will be documented quantitatively using the scoring of the MFM32 for the following: total score, domain 1 (standing and transfers), domain 2 (axial and proximal motor function), and domain 3 (distal motor function). The resulting scores will be listed by subject and summarized descriptively to compare between pre- and post-treatment.

Quality of Life Questionnaire: PROMIS-fatigue subscale questionnaires will be completed by participants during study visits 1 (Day -1), 2 (Day 14), and 3 (Day 27) with a raw score, theta, t-score, and standard error reported. All results will be listed by subject and summarized descriptively, as applicable, to compare between pre- and post-treatments.

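### Every participant in the 120 mg column was biopsied but only some in the 200 mg column, and the SAP's primary safety table separates neither procedure-related events nor the two visit schedules

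*SAP*

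**What the plan says.** **Who was biopsied.** The protocol synopsis reports that "Skeletal muscle tissue was obtained from the first six participants by needle biopsy" and adds "Additional biopsies are not needed". Protocol 11.1 gives the doses: "To date, three participants have been dose at 120 mg and three have been dosed at 200 mg". The revision history for Amendment 5 records "Removal of skeletal muscle needle biopsy procedure for subject 0007 and subsequent participants".

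**What later participants receive.** Protocol 9.5 states "The remainder of participants will be dosed at the same high dose". The 120 mg participants may re-enrol at the high dose.

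**Visits.** Amendment 5 also made Day 14 remote, dropped its ECG and made Day 42 an on-site visit. Protocol 11.1 follows the new pattern. SAP section 3 still has an inpatient mid-intervention visit and a remote last contact.

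**What the SAP assumes.** SAP 8.1 still says "All participants will undergo two needle muscle biopsies during the study", with the first before dosing (Day -1/Day 1) and the second at Day 27/28. SAP section 9 declares the SAP aligned with the protocol.

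**How events are counted.** Under SAP 6.3, a TEAE is any AE that starts or worsens at or after dosing, and "Each TEAE will be attributed to a treatment based on the onset date and time of the AE". Table 14.3.1.4 shows the primary composite by treatment. SAP Table 5.1 makes 200 mg in patients a single treatment, B. Relationship to drug is tabulated separately in Table 14.3.1.3. The causality scale in protocol 12.10.7.4 rates relationship to drug only and has no procedure category.

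**The concern.** The composite does not depend on cause, so a biopsy complication of grade 2 or more, or a serious one, counts in the same way as a drug effect. That would matter little if the two dose columns had the same exposure to biopsy. They did among the first six participants, but each later high-dose course adds an unbiopsied person to the 200 mg column and none to the 120 mg column.

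The effect of biopsy events is to raise the 120 mg rate relative to 200 mg. A true increase in events at 200 mg could then look smaller than it is, or absent. With three people at 120 mg, one procedural event moves that column by 1/3, or 33 points, so a reader needs to see what kind of event it was.

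The change of visit schedule falls on the same boundary, so the opportunity to detect AEs also differs between the columns.

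**Working it through.** **1. Count check.** Three at 120 mg plus three at 200 mg is six, which matches the six biopsied participants in the synopsis.

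**2. Size of the 200 mg column, n.** The protocol's target is about 8 to 20 completers in total, including the three at 120 mg.
- Without re-enrolments on top: 8 − 3 = 5, up to 20 − 3 = 17.
- With three re-enrolments added to 8 to 20 distinct completers: 5 + 3 = 8, up to 17 + 3 = 20.

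**3. Which biopsy events reach the composite.** They must be grade 2 or more, serious, or an AESI. Grade 1 soreness does not enter.
- Biopsy 2 (Day 27/28) comes after the first dose, so its events are treatment-emergent. This is the main route.
- Biopsy 1 precedes dosing, so its events count only if they start or worsen after dosing, or if they are dated to the dosing day with no onset time. SAP 6.3 treats the latter as treatment-emergent.

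**4. Expected gap with no drug effect.** Let b be the added fraction of biopsied people who have a qualifying biopsy event, with the same background rate in both columns.
- Added rate at 120 mg: b × 3/3 = b.
- Added rate at 200 mg: b × 3/n.
- Gap, 120 mg minus 200 mg: b × (1 − 3/n).

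The documents give no value for b. The table takes 10%, with 5% to 30% as the range.

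| n at 200 mg | Biopsied share | Gap, b = 5% | Gap, b = 10% | Gap, b = 30% |
|---|---|---|---|---|
| 3 (first six only) | 100% | 0 | 0 | 0 |
| 5 | 60% | 2.0 | 4.0 | 12.0 |
| 8 | 38% | 3.1 | 6.2 | 18.8 |
| 17 | 18% | 4.1 | 8.2 | 24.7 |
| 20 | 15% | 4.3 | 8.5 | 25.5 |

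Gaps are in percentage points. Example: 0.10 × (1 − 3/5) = 0.040.

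**5. Chance that it shows at all.** The probability of at least one biopsy event among the three at 120 mg is 1 − (1 − b)³: 14% at b = 5%, 27% at 10%, 49% at 20% and 66% at 30%.

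**6. Against sampling error.** One event in three people has an exact (Clopper-Pearson) 95% interval of 0.8% to 90.6%, far wider than any gap in the table.

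**7. After the fix.** Within the biopsied six, or with the 200 mg column split by biopsy status, the like-for-like gap due to biopsy is b × (1 − 3/3) = 0 for any b.

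**The case against.** The strongest reply is that no dose comparison is planned. The primary hypothesis concerns overall safety and tolerability. TEAEs are summarised by treatment and for the study overall, and the only AE comparison that SAP 6.3 names is descriptive, against historical controls. Relationship to drug is rated for every AE, listed by subject and tabulated. Events appear by preferred term, and a biopsy listing is planned (Appendix 16.2.5.4), so in a study this small a biopsy-site event would probably be noticed. Protocol 13.3 also mentions summaries by cohort and treatment, and the SAP has yet to write its safety table shells.

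Much of this stands. The problem is one of display, and no planned test is invalidated. But the relatedness table counts events over all TEAEs rather than subjects with the primary composite, and it cannot separate procedure-related events from other events unrelated to drug. Protocol 13.3 does not define cohort, and the SAP drops the term when it describes the AE tables.

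A reader might infer more than the documents support:
- *That the SAP ascribes every post-dose event causally to dose.* The quoted rule decides the table column; causality is assessed separately.
- *That dose and biopsy are fully confounded.* Three participants at 200 mg were also biopsied.
- *That only a minority at 200 mg is biopsied.* At n = 5 it is 60%.
- *That the historical comparison is inflated.* The documents do not say whether those controls had biopsies.
- *That biopsies distort CK, AST and ALT.* SAP 8.3 places laboratory tests at Screening and Days 14, 27 and 35, and does not say whether Day 27 blood comes before the Day 27/28 biopsy.
- *That the visit changes favour one dose.* AEs were assessed around Days 14 and 42 under both schedules, and no direction can be given.

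**Conclusion.** The concern holds as a partial, descriptive bias in the primary-endpoint display. Biopsy exposure is 100% at 120 mg and will be 15% to 60% at 200 mg once 8 to 20 participants have completed, depending on recruitment and re-enrolment. The spurious excess at 120 mg is 4.0 to 8.5 points at b = 10%, and 2.0 to 25.5 points over b = 5% to 30%.

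This rests on three assumptions: that all six had both biopsies as SAP 8.1 describes, that background rates are equal in the two columns, and that b lies in the stated range, for which the documents offer no figure. The counts and the direction for biopsy events are firm; the size is not.

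The bias is smaller than sampling error and does not invalidate the study's overall safety conclusion. It deserves correction because it runs in the direction that could hide a dose-related increase, and because the SAP has to be brought up to Amendment 5 in any case.

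**What to change.** In SAP 6.3 and Table 14.3.1.4:
1. Add a procedure-related flag for TEAEs (biopsy, cannulation) and show the primary composite with and without flagged events.
2. Split the 200 mg column into biopsied participants (before Amendment 5), later drug-naive participants and re-enrolled participants. Label the 120 mg column as all biopsied.
3. Add the like-for-like display of the biopsied six, three against three, as a supplement. It should not replace the full table, because three against three can show very little alone.

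In SAP 8.1, restrict the biopsy statement to the first six participants. Bring the visit description in SAP section 3 into line with Amendment 5, and revise the alignment statement in SAP section 9.

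The cost is SAP wording, one AE flag and extra columns in shells that are not yet written. The drawback is smaller cells in an already small table.
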